5.3.2 CLINICAL LABORATORY ASSESSMENT

Not applicable.

5.3.3 OTHER SAFETY ASSESSMENT

Not applicable.

6 STATISTICAL ANALYSES

6.1 ANALYSIS METHODS

6.1.1 ANALYSIS OF THE PRIMARY EFFICACY ENDPOINT(S)

Primary efficacy endpoint is ulcer healing at 12 weeks, defined as complete epithelialization which is maintained for a minimum of 14 days (as required by the FDA).³¹ Healing is thus a single endpoint assessed on a nominal scale.

Ulcer healing will be assessed by the cast technician at the local hospital who redress the DFU, approximately 1-2 times per week (depending on the status of the DFU) in both groups. The cast technician will also photograph the DFU so it can be assessed by another person, blinded to group allocation.

In the analysis of the primary endpoint, the ITT dataset (analyzed with and without adjustment for covariates) and the per protocol dataset (analyzed without adjustment for covariates only) will be used. For the non-adjusted analyses, crude risk ratio (RR) or OR will be calculated to assess the impact of offloading device type on ulcer healing. For the adjusted analysis, baseline variables (sex, age, education level, living conditions, diabetes type and duration, glycemic control, BMI, history of previous foot ulcers and amputations, foot deformities, index foot ulcer characteristics, number of active ulcers, use of tobacco, peripheral artery disease, and neuropathy, see point 5.1) will be included as candidates in a logistic multiple regression, using backward selection and a p-value of 0.10 as cut-off for removal.

Participants for whom the 12 week observation is missing will be categorized as “not healed”. The statistician conducting the analysis will be blinded to group allocation.

The proportion of healed ulcers in each study group will be calculated, and the results will be presented as RR or OR and corresponding 95% CI.

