3.2 ADHERENCE AND PROTOCOL DEVIATIONS

Adherence to the interventions (sealed shoe and TCC) is defined as continuous use of the devices during the treatment period. If a person treated with TCC removes the device on one or more occasions or refuses to continue treatment this will be considered non-adherence. If a person treated with a sealed shoe removes the device (assessed by inspecting if the seal has been broken) on one or more occasions or refuses to continue treatment this will be considered non-adherence.

Non-adherence will be presented per type of non-adherence and frequency. All types of non-adherence will be presented as number and percentage. In addition, removal of devices will be presented as means and standard deviation.

A protocol deviation is defined as a failure to adhere to the protocol such as the wrong intervention being administered, incorrect data being collected and documented, errors in applying inclusion/exclusion criteria or missed follow-up visits. This will be presented as number and type, per study group.

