3.3 ANALYSIS POPULATIONS

The primary outcome (ulcer healing) will be analyzed both on the ITT dataset, that is, on all randomized participants, and on the per protocol dataset, including only patients who were exposed to the intended intervention at least 80% of the treatment days, as judged per above (point 3.2). Secondary outcomes (including adverse events and adverse device effects) will only be analyzed on the ITT dataset.

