6.1.8 SENSITIVITY ANALYSES

The primary outcome will be analyzed on the ITT data set, per protocol dataset, and ITT dataset using multiple regression as a sensitivity analysis to test the robustness of the results. Multiple imputation will also be used as a sensitivity analysis for the primary outcome (see point 6.2).

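### The per-protocol analysis of healing is limited to a crude comparison, which leaves the one comparison not protected by randomisation open to measured selection bias of unknown direction

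*SAP*

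**What the plan says.** SAP 3.3 has the primary outcome analysed on two sets: it "will be analyzed both on the ITT dataset, that is, on all randomized participants, and on the per protocol dataset". The second set is defined as "including only patients who were exposed to the intended intervention at least 80% of the treatment days", with exposure judged by the adherence rules in SAP 3.2.

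SAP 6.1.1 then treats the two sets differently: "the ITT dataset (analyzed with and without adjustment for covariates) and the per protocol dataset (analyzed without adjustment for covariates only) will be used". The crude analysis is a risk ratio or odds ratio. In the adjusted ITT analysis the baseline variables "will be included as candidates in a logistic multiple regression, using backward selection and a p-value of 0.10 as cut-off for removal".

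SAP 6.1.8 repeats the list: "The primary outcome will be analyzed on the ITT data set, per protocol dataset, and ITT dataset using multiple regression as a sensitivity analysis". An adjusted per-protocol analysis appears nowhere, and no reason is given. Nor do the documents say which set decides non-inferiority, or whether ITT and per-protocol must both meet the margin.

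The material for adjustment exists. SAP 5.1 lists the baseline variables collected, and SAP 2.2 makes ulcer area (below or above 1 cm²) a randomisation stratum.

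**The concern.** Randomisation makes the ITT arms comparable apart from chance, so covariates there mainly add precision. The per-protocol set is chosen on behaviour after allocation. If adherence is related to healing prognosis, and related differently in the two arms, the retained groups differ at baseline and a crude comparison mixes that difference with the device effect.

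Different selection by arm is plausible. The Background in both documents says that some patients do not accept casting and that it is harder for working patients and for older people with gait or balance problems, whereas the shoe is meant to leave daily activity unchanged. Adherence is also detected differently: in the shoe arm, removal is read from the seal.

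In a non-inferiority trial the per-protocol result is a main check on ITT. If selection shifts it, it can agree with a wrong ITT result, or contradict a right one, for reasons unrelated to the devices.

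**Working it through.** The plan gives no per-protocol figure to reproduce, and no adherence rates. The retention and stratum-specific healing figures below are therefore assumptions.

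**Inputs from the SAP.** Healing 90% in both arms, margin 10 points, 80% power and 112 participants as 56 per group (2.3); one-sided testing at 95% confidence (3.1).

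**The SAP's sample size.** The usual formula gives n = (1.645 + 0.842)² × (2 × 0.9 × 0.1) / 0.10² ≈ 111.3, so 112 *per arm*. The SAP uses 112 as the total. That is a separate matter, but it is why results are shown for both 56 and 112 per arm.

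**Assumptions.** Half the ulcers are small and half large. TCC heals 98% of small and 82% of large ulcers (mean 90%). The shoe is truly 10 points worse in each stratum (88% and 72%). Healing depends on stratum and arm, not on adherence, and no outcome is missing.

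**Formula.** Let q be the share of large ulcers among those retained in an arm. The strata differ by 16 points in healing within each arm, so

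crude per-protocol difference = -0.10 + 0.16 × (q_TCC - q_shoe).

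| Retained small/large, shoe | Retained small/large, TCC | q_shoe | q_TCC | Crude difference |
|---|---|---|---|---|
| 95% / 70% | 80% / 90% | 0.70/1.65 = 0.424 | 0.90/1.70 = 0.529 | -8.3 points |
| 80% / 90% | 95% / 70% | 0.529 | 0.424 | -11.7 points |
| 95% / 70% | 95% / 70% | 0.424 | 0.424 | -10.0 points |
| 95% / 80% | 90% / 85% | 0.80/1.75 = 0.457 | 0.85/1.75 = 0.486 | -9.5 points |

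The shift is additive. With truly equal devices, the second row would show 0.16 × (0.424 - 0.529) = -1.7 points against the shoe.

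**Stratified estimate.** The Mantel-Haenszel risk difference is Σ w_k d_k / Σ w_k, with w_k = n_shoe,k × n_TCC,k / (n_shoe,k + n_TCC,k). Each d_k is -0.10 here, so it returns -10.0 whatever the retention.

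**If the per-protocol set alone decided** (simulation, nominal one-sided 5%). In the first row the crude analysis falsely passes in about 9% of trials at 56 per arm and 10% at 112. In the second row it falsely passes in 3.6% and 2.7%. With stratification, the first row falls to 6-7%.

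**If ITT and crude per-protocol must both pass.** The probability that both pass cannot exceed the probability that ITT passes. In simulations of the first row, ITT alone falsely passed in 5.3-5.7% of trials, and both together in 4.6% (56 per arm) and 4.7% (112 per arm).

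**If the prognostic factor is poorly measured.** Take another pattern: shoe retention 95% good / 50% poor prognosis, TCC 95% in both. Crude per-protocol averages -7.5 points. Adjustment restores about -10 if the factor is fully measured, reaches only -8.1 if it is partly measured, and stays at -7.5 if it is unmeasured.

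**How much adjustment the data can carry.** At 56 per arm, the first row retains 56 × 0.825 + 56 × 0.85 = 46.2 + 47.6 ≈ 94 patients. At 90% healing that is about 9 unhealed ulcers.

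**The case against.** A reader might infer that the crude per-protocol analysis will produce a false non-inferiority claim. The documents do not support that, for two reasons. First, they do not make the per-protocol set the sole deciding analysis: SAP 3.3 uses both sets, and SAP 6.1.8 lists the analyses as robustness checks. Read jointly with ITT, a biased per-protocol result cannot raise the false non-inferiority rate. Second, nothing fixes the direction. The remarks about who finds casting difficult do not tie non-adherence to ulcer size or healing prognosis, and the reverse pattern makes the per-protocol test conservative. Both arguments stand, though the first depends on a decision rule that the SAP leaves unstated. Even under that rule, a biased per-protocol result could still contradict a correct ITT result.

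It can also be said that a crude per-protocol analysis is a reasonable, simple choice in a trial of this size, and that adjustment may reassure falsely. This stands in part. About nine unhealed ulcers will not support a model with many covariates and site, and adherence may depend on behaviour that no baseline ulcer variable captures. It argues for a very small adjustment reported beside the crude result, rather than for no adjustment.

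Finally, there are gaps upstream. SAP 3.3 asks for a percentage of days but refers to SAP 3.2, which counts removal occasions. The margin is a 10-point difference, while results are reported as risk or odds ratios. Both are true, and adjustment mends neither.

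**Conclusion.** The point holds as a modest one. SAP 6.1.1 adjusts the comparison that randomisation protects and leaves crude the one that it does not, without a stated reason and with the covariates to hand. Under the assumptions above the crude result moves by about 1.7 points either way against a 10-point margin, and by nothing if selection is the same in both arms. These figures show what is possible and do not forecast this trial. The consequence is a per-protocol result that may wrongly support or wrongly contradict ITT. An inflated false non-inferiority rate would follow only if per-protocol could carry the conclusion by itself and the selection ran in the shoe's favour. This is a cheap improvement to consider, not a flaw that undermines the primary analysis.

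**What to change.** In SAP 6.1.1, delete *only* from the per-protocol restriction and prespecify an adjusted per-protocol analysis:

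- a risk difference with its confidence interval, on the scale of the 10-point margin, stratified by the ulcer-size randomisation stratum (for example Mantel-Haenszel);
- at most one or two further baseline prognostic factors, fixed in advance (for example peripheral artery disease), with no backward selection;
- reported beside the crude per-protocol result, with a statement that it removes measured confounding only.

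Add the analysis to the list in SAP 6.1.8. Fix the wording before outcome data are seen, since an adjusted per-protocol analysis added later would look post hoc.

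The cost is one extra analysis, no new data and some loss of precision. The few unhealed ulcers rule out a longer covariate list. How ITT and per-protocol combine in the non-inferiority decision is a separate rule that the SAP still needs to state.

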2.3 SAMPLE SIZE

The sample size calculation was performed using <http://powerandsamplesize.com/Calculators/Compare-2-Proportions/2-Sample-Non-Inferiority-or-Superiority>. Primary outcome is proportion of healed ulcers after 12 weeks of treatment. Based on the literature and our feasibility study the proportion of healed ulcers after 12 weeks treatment is estimated to 90% with sealed shoe or TCC.^{15, 16} If accepting $p=0.05$, a statistical power of 80% and a non-inferiority limit of 10%, 112 participants are

needed. To compensate for attrition of participants during the long-term follow up of secondary outcomes, the aim is to recruit 150 participants. The participants will be randomized to treatment with sealed therapeutic shoe or TCC. However, if it turns out that it is too difficult to recruit 150 participants, the recruitment of participant will end when the primary end point (healing at 12 weeks) has been observed for 56 participants per group, giving a total of 112 which fulfils the sample size calculation.

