2.4 FRAMEWORK

The primary outcome will be tested according to the non-inferiority hypothesis testing framework. All secondary outcomes will be tested according to the superiority hypothesis testing framework.

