3 STATISTICAL PRINCIPLES

3.1 CONFIDENCE INTERVALS AND P VALUES

In all analyses a 95% confidence level will be used as a cut off to declare statistical significance, and report both exact p-values and 95% CI. One-sided tests and CI will be used for the primary outcome and two-sided tests and CI the secondary outcomes. No adjustment for multiple comparisons will be used.

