4.3 RECRUITMENT

Information required by the CONSORT flow diagram will be collected and presented: number of patients screened, number who were excluded (per reason) and number who declined to participate, number of patients randomized, number of participants who were allocated to each study group, number who received the allocated intervention and number who did not receive the allocated intervention (per reason and study group), number who discontinued intervention or were lost to follow-up (per reason, per follow-up visit and per study group), number who were analyzed and excluded from analysis (per reason and study group).

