4.4 WITHDRAW / FOLLOW-UP

There are several timings of possible withdrawal/lost to follow-up: before base-line assessment, before the intervention has been administered, during the intervention period, and before each follow-up assessment. Reasons include, but are not restricted to, clinical reasons, death, refusal to continue treatment or follow-up, unable to make contact with the participant, etc.

Number of participants, reasons and timing of withdrawal/lost to follow-up will be presented by intervention arm in a CONSORT flow diagram (point 4.3)

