6.1.2 ANALYSIS OF THE SECONDARY ENDPOINT(S)

The secondary analyses are not dependent on the findings of the primary endpoint. No adjustment for Type 1 errors will be used as only one or a few statistical tests will be conducted for each secondary endpoint.

The secondary endpoints are time to healing and measures listed in Table 1. Each secondary endpoint is measured between one and five occasions during the study. The ITT dataset will be used for all analyses of secondary endpoints. Adjusted analyses will only be conducted for certain secondary endpoints that are of particular interest.

Time to healing will be compared between the study groups using survival analysis. Kaplan-Meier survival curves will be produced for the two study groups with median healing times and 95 % CI. Participants for whom the ulcer has not healed will be treated as censored and their date of trial exit or date of last available assessment will be used to calculate their duration in the trial. Hazard ratio with

95% CIs will be presented. Treatment effect will be explored using a Cox proportional hazards model including stratification factors (ulcer area and depth at baseline, periphery artery disease and infection grade) initially.

Survival analysis as above (but without adjustment) will also be used to compare ulcer recurrence after healing between the study groups. Recurrence rates at 12 months after healing will also be compared.

The analysis of the other secondary endpoints will be conducted according to scale level (nominal, ordinal or interval; Table 1) and compared at each time point (base-line, 4 weeks into treatment and 1, 6 and 12 months post-treatment) using the ITT dataset without adjustment for covariates: t-tests for ordinal and interval data if the assumptions of the t-test is fulfilled (normal distribution and equal variances), otherwise Wilcoxon rank sum test will be used. The Chi-squared test or generalized linear regression method will be used for nominal scale data. For each comparison both exact p-values and two-sided 95% CI will be reported.

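### Counting missing 12-week outcomes as not healed is not reliably conservative for non-inferiority; the SAP neither varies that assumption by arm nor says what follows if imputation disagrees

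*SAP*

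**What the plan says.** SAP 2.4: "The primary outcome will be tested according to the non-inferiority hypothesis testing framework". SAP 3.1: "One-sided tests and CI will be used for the primary outcome". The limit is 10% and the error level 5% (SAP 2.3), and the planning assumption is that "the proportion of healed ulcers after 12 weeks treatment is estimated to 90% with sealed shoe or TCC".

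For missing outcomes, SAP 6.1.1 says "Participants for whom the 12 week observation is missing will be categorized as" not healed, in both arms.

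Several other provisions bear on this:

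- SAP 6.1.8: "Multiple imputation will also be used as a sensitivity analysis for the primary outcome". SAP 6.2 repeats this with a reference to an earlier device study, but states no imputation model and no missingness assumption.
- SAP 3.3, 6.1.1 and 6.1.8 plan a per-protocol analysis of healing, and SAP 3.2 counts refusal to continue treatment as non-adherence.
- SAP 4.3 reports the "number who discontinued intervention or were lost to follow-up (per reason, per follow-up visit and per study group"), and SAP 4.4 says "reasons and timing of withdrawal/lost to follow-up will be presented by intervention arm".
- For time to healing, SAP 6.1.2 says: "Participants for whom the ulcer has not healed will be treated as censored".

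Neither document gives an expected loss rate at 12 weeks. SAP 2.3 ties its attrition allowance to the long-term secondary outcomes.

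**The concern.** Counting missing as failure is often taken as the cautious choice. In a non-inferiority trial it also lowers the comparator's healing rate. Each lost TCC participant who would have healed makes TCC look worse, and so makes a truly inferior shoe look closer to it. The rule can therefore err in either direction, depending on how many are lost in each arm and how many of them would have healed.

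At stake is the primary claim. If the shoe is truly worse by the full limit, the primary analysis could declare non-inferiority more often than the planned 5%. Imputation may then give a different answer, and the SAP does not say how the report should treat that.

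**Working it through.** **Scale.** The plan does not state the scale of the 10% limit. With 90% healing in both arms, one-sided 5% and 80% power, the usual risk-difference formula gives (1.645 + 0.842)² × 2 × 0.9 × 0.1 / 0.10² = 111.3, so 112. That matches the plan's number, which supports reading the limit as 10 percentage points. The formula's 112 is per group whereas SAP 2.3 uses 112 in total. That mismatch is a separate matter and is not pursued here.

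**How the rule acts.** Let p be true healing, L the proportion lost and h the healing the lost would have had. The analysed healing rate in each arm is p − L·h. The analysed difference, shoe minus TCC, is therefore

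true difference + (L·h for TCC − L·h for shoe).

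The rule moves the result towards non-inferiority when the TCC product is the larger. If none of the lost would have healed, both products are zero and nothing shifts.

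**Size.** Inputs: true healing 80% shoe and 90% TCC (TCC at the planning rate, shoe worse by exactly the limit), 75 per group (half of 150), and a one-sided 95% Wald lower limit compared with −10 points. Probabilities come from exact binomial enumeration. Loss rates and h are assumptions. Without loss, false non-inferiority is 5.6%; the excess over 5% comes from the Wald interval.

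| Loss shoe / TCC | Lost heal at own arm's rate | 50% | 25% |
|---|---|---|---|
| 3% / 5% | 9.9% | 7.5% | 6.5% |
| 5% / 10% | 19% | 11% | 8.1% |
| 5% / 15% | 39% | 19% | impossible |
| 10% / 10% | 6.7% | 5.2% | 5.4% |
| 10% / 5% | 1.6% | 2.2% | 3.5% |

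Example for 5% / 10% at the arm's rate: shoe 0.80 − 0.05 × 0.80 = 0.76; TCC 0.90 − 0.10 × 0.90 = 0.81. The 10-point deficit becomes 5 points.

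The impossible cell would need (0.90 − 0.15 × 0.25) / 0.85 = 101.5% healing among observed TCC participants. The 50% cell in that row needs 97.1%, so it is possible but strained.

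A Newcombe limit gives similar values at 75 per group: 5.2% without loss, 18.7 / 10.9 / 7.8% for 5% / 10% loss, and 39.1 / 19.4% for 5% / 15%. With 56 analysed per group, the first two rows become 9.5 / 7.3 / 6.5% and 17 / 10 / 7.9%, against 5.7% without loss. SAP 2.3 counts 56 observed outcomes, so slightly more than 56 would be randomized; this changes little.

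**The other direction.** If the devices are truly equal at 90%, 10% loss in both arms lowers power at 75 per group from 67% to 47% (arm's rate) or 54% (lost healing at 50%). Here the rule works against the shoe.

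**Would planned imputation show it?** As a stand-in for imputation that assumes loss unrelated to outcome, I analysed observed cases only. By simulation, among trials where the primary rule falsely declares non-inferiority, the observed-case analysis misses the limit in:

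- about 53% at 3% / 5% loss (arm's rate);
- about 74% (arm's rate) and 85% (50%) at 5% / 10% loss;
- about 86% (arm's rate) and 97 to 98% (50%) at 5% / 15% loss.

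The stand-in can itself fail when loss is related to outcome. Suppose 20% are lost in both arms, shoe participants heal at 90% if observed and 40% if lost, and TCC participants heal at 90% throughout. The true shoe rate is 0.8 × 0.90 + 0.2 × 0.40 = 80%, so the true difference is −10 points. False non-inferiority at 75 per group is then 39% with the primary rule and about 59% with observed cases.

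**Worked example (assumed counts, 75 per group).** Shoe: 63 healed, 8 not, 4 missing. TCC: 62 healed, 5 not, 8 missing. Healing assigned to the missing is treated as fixed.

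| Assumption for missing | Lower limit (points) | Limit met? |
|---|---|---|
| Not healed (84.0% vs 82.7%) | −8.7 | yes |
| 25% heal, both arms | −9.5 | yes |
| 50% heal, both arms | −10.3 | no |
| Each arm's observed rate | −11.6 | no |
| Observed cases only | −11.9 | no |

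**The case against.** The strongest reply is that the plan already covers this. Multiple imputation replaces the not-healed assumption, the per-protocol analysis gives a further view, and losses are shown by arm, reason and timing. The outcome is binary, so a reader with those counts could build a simple grid unaided. Participants are seen once or twice a week, so loss by week 12 may be small.

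Much of this stands. A reader might infer that the planned output could never reveal the problem. The documents do not support that: the observed-case proxy catches most false claims at the larger imbalances and already reverses the worked example. Detection is weakest at 3% / 5% loss, where the inflation is also smallest.

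A reader might also infer that the rule generally favours the shoe, or that TCC will lose more participants because SAP 1.1 says not everyone accepts a cast. Neither follows. Stopping a device is not the same as a missing outcome, refusal is foreseen in both arms, and no loss rate is given. Nor is greater TCC loss by itself the condition: it is the product of loss and healing among the lost that counts, and the two arms can differ in either.

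What the reply leaves open is narrower. Imputation that assumes loss unrelated to outcome cannot show what happens when loss is related to outcome in one arm. The SAP also gives a disagreement between imputation and the primary result no consequence.

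**Conclusion.** The point holds in a limited form. The not-healed rule is acceptable as the primary analysis but should not be presented as conservative. Under modest assumed imbalance towards TCC loss, false non-inferiority rises from 5.6% to between 6.5% and 19%. It reaches 39% only at 5% / 15% loss with the lost healing at their arm's rate. Equal loss has little effect when the lost heal alike or at their own arm's rate, and more shoe loss makes the test stricter.

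The remaining gaps are the absence of an arm-specific analysis and of any stated consequence if imputation disagrees. These sizes rest on assumed loss rates, assumed healing among the lost, a true deficit of exactly 10 points, the risk-difference scale and a Wald limit; the imputation figures rest on an observed-case proxy. This is worth correcting before the data are analysed, but it does not undermine the design.

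**What to change.** Keep the primary rule and make these changes:

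1. In SAP 6.1.8, add one prespecified tipping-point analysis on the risk difference against the same 10-point limit. Vary the healing rate of missing participants separately by arm, from 0 to the rate observed in that arm, and show the combinations at which non-inferiority is lost beside the primary result.
2. Do not make this a condition for success. The harshest corner (missing shoe not healed, missing TCC at the observed TCC rate) meets the limit only about 8% of the time with equal devices at 90%, 75 per group and 10% loss in both arms, against 47% for the primary rule.
3. State that if the multiple imputation result does not meet the limit, the report will say that the non-inferiority conclusion depends on the missing-data assumption.
4. As minor clarifications, count an ulcer with confirmed healing by week 12 as healed even if no visit falls at week 12 (SAP 6.1.1), and include arm in the imputation model (SAP 6.2).

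The cost is a few SAP sentences, a little more analysis and a possibly less favourable sensitivity result. No new data are needed, since ulcer status is already recorded at the technician visits.

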Aim 2. To investigate whether there is a difference in adverse events during the treatment period with sealed shoe and TCC.

Aim 3. To investigate whether there is a difference in long-term effects (up to 12 months after end of treatment) with sealed shoe and TCC.

Aim 4. To investigate whether there is a difference in health economic outcomes between treatment with sealed shoe and TCC.

The null hypothesis is that a sealed therapeutic shoe does not heal DFUs as effectively as TCC, and that there are no differences between sealed shoe and TCC in adverse events, long-term effects and health economic outcomes.

Methods

The study is a non-inferiority multicenter randomized controlled trial (RCT).

Participants

Inclusion criteria: at least 18 years old, diagnosed diabetes mellitus (all types) and foot ulcer under metatarsal heads. A foot ulcer is here defined as "a break of the skin of the foot that includes minimally the epidermis and part of the dermis."¹⁵

Exclusion criteria: large ulcers (covering 3-5 metatarsal heads), toe pressure or TcPO₂ <30 mmHg, infection of IWGDF grade 3 (if uncontrolled or treatment has not been administered) or IWGDF grade 4, life expectancy <1 year, active Charcot foot, need of custom-made shoe,

and inability to read or write Swedish. In addition, people will be excluded where dementia, language- or other communication difficulties, active alcohol or substance abuse, or other factors increase the risk that adverse events will not be noted or reported, if the person does not have adequate social support.

The study is a randomized controlled non-inferiority trial where it will be investigated whether a new intervention (sealed shoe) is at least as effective as the established intervention (TCC).

Primary outcome is proportion of healed ulcers after 12 weeks of treatment. Based on the literature and our feasibility study the proportion of healed ulcers after 12 weeks treatment is estimated to 90% with sealed shoe or cast.^{16,17} If accepting $p=0.05$, a statistical power of 80% and a non-inferiority limit of 10%, 112 participants are needed. To compensate for attrition of participants, the aim is to recruit 150 participants. However, if it turns out that it is too difficult to recruit 150 participants, the recruitment of participant will end when the primary end point (healing at 12 weeks) has been observed for 56 participants per group, giving a total of 112 which fulfills the sample size calculation.

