1.2 HYPOTHESES AND OBJECTIVES

The overarching objective is to evaluate whether sealed shoe can heal DFU at least as effectively as TCC, but with fewer adverse events during the treatment period, better long-term effects and to a lower cost.

Specific objectives

Objective 1. To investigate whether a sealed shoe can heal DFUs at least as effectively as TCC (non-inferiority, one-sided hypothesis testing).

Objective 2. To investigate whether there is a difference in adverse events during the treatment period with sealed shoe and TCC (superiority, two-sided hypothesis testing).

Objective 3. To investigate whether there is a difference in long-term effects (up to 12 months after end of treatment) with sealed shoe and TCC (superiority, two-sided hypothesis testing).

Objective 4. To investigate whether there is a difference in health economic outcomes between treatment with sealed shoe and TCC (superiority, two-sided hypothesis testing).

The null hypotheses are that a sealed therapeutic shoe does not heal DFUs at effectively as TCC, and that there are no differences between sealed shoe and TCC in side-effects, long-term effects and health economic outcomes.

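### SAP 6.1.1 plans the primary comparison as a risk ratio or odds ratio, but the only non-inferiority margin is 10% on healed proportions, and no rule links the two

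*SAP*

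**What the plan says.** **Framework.** SAP 1.2 sets the healing objective as "non-inferiority, one-sided hypothesis testing". SAP 2.4 adds: "The primary outcome will be tested according to the non-inferiority hypothesis testing framework". SAP 3.1 specifies one-sided tests and intervals for the primary outcome at the 95% level.

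**Margin.** The sample-size text is the only place that gives one. The protocol (Methods, Participants) has "a statistical power of 80% and a non-inferiority limit of 10%, 112 participants are needed", and SAP 2.3 repeats the figures. The limit follows directly on the planning assumption that "the proportion of healed ulcers after 12 weeks treatment is estimated to 90% with sealed shoe or TCC". Its scale is not named.

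**Final analysis.** The protocol leaves the statistical analysis to the SAP. SAP 6.1.1 says that, without adjustment, "crude risk ratio (RR) or OR will be calculated to assess the impact of offloading device type on ulcer healing". The adjusted analysis is a logistic regression. The healed proportion in each group is also calculated, and "the results will be presented as RR or OR and corresponding 95% CI". Section 6.1.1 does not mention the 10% limit.

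**Elsewhere.** A risk difference with a confidence interval is named only for the interim analysis (SAP 2.5). The test there is a two-sided chi-square at the 0.001 level, not a comparison with the margin. SAP 3.3 and 6.1.8 have the primary outcome analysed on both the ITT and the per-protocol sets, without saying what follows if the two disagree.

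**The concern.** A non-inferiority conclusion comes from setting one confidence limit against one margin on the same scale. Here the margin sits on the scale of proportions and the planned comparison sits on a ratio scale, with the choice between two ratios left open. A 10-point margin has no fixed equivalent as a ratio, because the conversion depends on the control healing rate. Someone would therefore have to choose the measure, and convert the margin if a ratio is used, after the SAP is final. If that choice can change the verdict on the same data, the primary conclusion is not fully fixed in advance.

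**Working it through.** **1. Which scale does the 10% belong to?** Inputs from SAP 2.3 and 3.1: 90% healed in each arm, limit 0.10, one-sided 0.05, power 80%. On the difference scale:

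n per arm = (1.645 + 0.842)² × (0.90×0.10 + 0.90×0.10) / 0.10² = 6.185 × 0.18 / 0.01 = 111.3, i.e. 112.

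This is the plan's own number, so the limit was most likely an absolute difference. The same inputs on a log-ratio scale give 100 per arm (RR limit 0.889), 124 (RR limit 0.90) or 209 (OR limit 0.444). None of these is 112. The formula's 112 is per arm, whereas SAP 2.3 has "56 participants per group, giving a total of 112 which fulfils the sample size calculation". That is a separate problem. It lowers the absolute power figures below but is not part of this point.

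**2. What would the margin be on the ratio scales?** These conversions are mine and illustrative.
- At 90% control healing: RR = 0.80/0.90 = 0.889; OR = (0.80/0.20)/(0.90/0.10) = 4/9 = 0.444.
- At 80% control healing (assumed): RR = 0.70/0.80 = 0.875; OR = (0.70/0.30)/(0.80/0.20) = 0.583.

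The equivalent moves with the control rate, most of all for the OR.

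**3. One data set, three measures.** Take 50 of 56 healed in each arm (89.3%) and one-sided 95% Wald limits.
- Difference: 0 − 1.645 × √(2 × 0.8929 × 0.1071 / 56) = −1.645 × 0.0585 = −9.6 points. Above −10: pass.
- RR: exp(−1.645 × √(2 × (1/50 − 1/56))) = exp(−1.645 × 0.0655) = 0.898. Above 0.889: pass.
- OR: exp(−1.645 × √(2 × (1/50 + 1/6))) = exp(−1.645 × 0.611) = 0.366. Below 0.444: fail.

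**4. How often does the measure decide?** I enumerated every pair of binomial outcomes with true healing of 90% in both arms, using Wald limits and the margins converted at 90%. I added 0.5 to the cells for RR and OR only when a cell was zero.

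| | 56 per arm | 75 per arm |
|---|---|---|
| Declares non-inferiority: difference | 55.7% | 67.3% |
| Declares non-inferiority: RR | 60.9% | 70.9% |
| Declares non-inferiority: OR | 35.8% | 43.3% |
| Opposite verdicts: RR v OR | 25.6% | 27.8% |
| Opposite verdicts: difference v OR | 20.1% | 24.2% |
| Opposite verdicts: difference v RR | 5.5% | 3.6% |

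The contrasts between rows are what matter here.

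**5. Does the interval method matter?** At 50/56 v 50/56 the Wald limit for the difference is −9.6 points (pass) and the Newcombe score limit is −10.06 (fail). At a true 80% v 90%, the edge of the margin, the false-declaration rates are 5.7% (Wald) and 4.8% (Newcombe) with 56 per arm, and 5.6% and 5.2% with 75 per arm. Either is usable, but only one can be the rule.

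**The case against.** **The rule can be inferred.** A reader might conclude that the SAP as written cannot deliver a non-inferiority verdict at all. The documents do not support that. SAP 1.2 and 2.4 fix a one-sided non-inferiority test, 3.1 fixes the level, 2.3 puts a 10% limit beside healed proportions, and 6.1.1 yields the counts. A statistician could apply the usual rule, a lower limit above −10 points. This objection stands against the strong reading. It does not remove the gap: the rule is unwritten, and 6.1.1 names different measures.

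**An estimate on the margin's scale is planned.** Group proportions are on that scale, so it would be wrong to say nothing is. What is missing is the between-group difference with its interval.

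**The ratio margins are supplied by this review.** True. The disagreement rates describe a possible later conversion, not a planned one, and they come mainly from the OR. At a true 80% v 90% with 56 per arm the three measures behave alike: 5.7% (difference), 6.3% (RR) and 4.9% (OR). The close agreement of difference and RR also depends on the 0.889 conversion. If 10% were read as RR 0.90, 50/56 v 50/56 would fail on RR (0.898) and pass on the difference.

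**The analyst is blinded.** SAP 6.1.1 says: "The statistician conducting the analysis will be blinded to group allocation". This limits steering the measure towards one arm. It does not fix the measure in advance.

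**Requiring both analysis sets is a convention.** Agreed. SAP 6.1.8 can be read as making the other analyses robustness checks on the ITT result. The per-protocol set is also unclear: SAP 3.2 counts a single removal of the device as non-adherence, while 3.3 asks for exposure on at least 80% of treatment days as judged by 3.2. A both-sets rule should not be imposed by default.

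**Conclusion.** The point holds and should be corrected before the final analysis. For the trial's central claim, the SAP plans a comparison on a scale that has no margin, leaves two measures open, and states no decision rule. Under margins converted at 90%, those two measures give opposite verdicts in about 26% to 28% of trials when both arms truly heal 90%, and difference and OR do so in about 20% to 24%. Difference and RR disagree in only about 4% to 5%, so the exposure is mainly to the OR.

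These sizes assume that the 10% means percentage points, which step 1 supports but the documents do not state. They also assume conversion at the planned 90%, Wald limits, and 56 or 75 per arm. The gap in the text does not depend on them. Nothing in the documents suggests that the open choice was meant to favour either device.

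**What to change.** In SAP 6.1.1:

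- Make the primary measure the difference in healed proportions, shoe minus TCC, with the one-sided 95% lower confidence limit of SAP 3.1.
- Name one interval method in advance. Newcombe score is one suitable example.
- State the 10% limit as 10 percentage points, and declare non-inferiority only if the lower limit is above −10 points.
- Keep RR, OR and the logistic model as supportive analyses.
- State now whether the ITT set alone decides, with per-protocol as a robustness check, or both sets must meet the limit. If both, first reconcile the per-protocol definition between SAP 3.2 and 3.3.

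**Cost.** SAP wording only, with the same data and standard software. Using Newcombe instead of Wald lowers power at 90% v 90% from 55.7% to 51.0% (56 per arm) and from 67.3% to 62.8% (75 per arm). Requiring both sets costs more. If per-protocol were a random 90% or 80% of ITT (an assumption, since real adherence may differ by device and relate to healing), simulated power with Wald limits falls from 55.7% to 49.3% or 45.8% (56 per arm), and from 67.3% to 60.2% or 55.1% (75 per arm).
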